1- The concept that patients with autoimmune encephalitis respond rapidly to immunotherapy, and that most of the remaining symptoms a few months after disease onset are caused by irreversible brain alterations is inaccurate, as we recently reported for anti-NMDAR encephalitis (20). We postulate that the same occurs for anti-LGI1 encephalitis. In a recent prospective study in which 24 patients with anti-LGI1 encephalitis were invited to come to our center for additional clinical investigations during the chronic phase of the disease, we found that most (90%) had deficits in 1 or more of 6 cognitive domains at the first visit (V1), 65% had cognitive deficits at V2 (6 months), and 62% at V3 (1 year). In addition, at V1, about 90% of the patients had other symptoms (facio-brachial dystonic or focal seizures; REM sleep behavior disorder, insomnia) that were missed by patients, family members, or physicians. Some of these alterations were still present in 55% of patients at V2, and in 40% at V3. The main reason for the symptoms being unnoticed was that they often occurred at night or were identified with EEG or video-polysomnography.

Indeed, these studies showed that patients considered asymptomatic (regarding facio-brachial dystonic seizures, other seizures, or sleep disorder) had evidence of these types of symptoms with the appropriate tests. Because these clinical alterations were under-recognized, patients were no longer receiving immunotherapy or were undertreated with anti-seizure medications. These findings, which need to be confirmed and expanded with additional studies, are novel and important because they challenge the current prevailing view that facio-brachial dystonic seizures and other types of seizures, develop early in the course of the disease (often as first symptom) and resolve rapidly with immunotherapy (21). We also found that actimetry (or actigraphy assessed with a wrist-watch like device) may help to track these nocturnal seizures at home, an observation that we propose to assess in the current proposal.

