correlate with some of the seizures and sleep alterations (eg, awakenings, sleep fragmentation) noted during the in person visit and video-polysomnography. In practical terms for patients, it will be akin to wearing a wristwatch (patients will leave the hospital with the device placed in the non-dominant wrist and in use, so that they will not need further instructions) for 1 week at home (day and night) after each presential visit (V1, V2 and V3). At the end of the week, a courier will collect it, and over the course of the following month, the recordings will be downloaded and analyzed with the MotionWare software (CamTech Ltd., UK). Actimetry is a test used in routine clinical care in the sleep disorders clinic and can be requested from the SAP request form. As with other tests, actimetry studies are identified with the patient's history number. Once the files are downloaded, in the case of research studies, they are identified with the patient's study code and stored in the F:/ folder. Only principal investigators can access the patient-code relationship.

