Each visit consists of ~1 day and 1 night at Hospital Clínic (distributed in 1/2 day, 1 night, and 1/2 day) during which they undergo clinical assessments and tests according to a pilot study: neurologic and cognitive assessment, EEG, ANS, EMG, brainstem reflex study and video-polysomnography. At V2 we will obtain an MRI (to compare with that of the acute phase). We will also obtain and the blood and serum. During the post-acute stage (by the time that patients will come to Hospital Clínic de Barcelona), blood and CSF samples will be obtained for identical studies as those performed in the acute stage serum and CSF samples. Two lumbar punctures (LP) will be performed, after informed consent, one at the first presential visit (V1) and the other at the last presential visit (V3). After the first visit, patients/families will be instructed to keep remote cognitive training for 6 months. The frequency of cognitive training is suggested by data from our pilot study in which 90% of patients had cognitive abnormalities at V1 and the improvement (albeit partially; without cognitive training) mainly occurred during the first 6 months. These patients will serve as external controls.

Summary:

V1: neurologic and cognitive assessment, EEG, ANS, EMG, brainstem reflex study and video-polysomnography. Blood and serum examination. Lumbar puncture

V2: neurologic and cognitive assessment, EEG, ANS, EMG, brainstem reflex study and video-polysomnography. MRI. Blood and serum examination

V3: neurologic and cognitive assessment, EEG, ANS, EMG, brainstem reflex study and video-polysomnography. Blood and serum examination. Lumbar puncture

Presential visits

- Presential standard neuropsychiatric examinations and cognitive assessments will be conducted as per routine clinical practice and with a reported panel of neurological functional, cognitive and psychiatric tests. Total time ~4h spread over 3 visits (the exact timetable can be adapted to patients' preferences and the length of the interviews will vary according to patients' clinical status; the times are indicative and are overestimated to be sure). These clinical evaluations will take place in the same room where the patients will sleep, and patients will have enough pauses in between to rest, eat/drink and go for a walk outside the hospital with their relatives.

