- Psychophysical testing of working memory: The duration of this task depends on the performance of the patients; maximum ~1:30h. It will be done in the same room during V1 (1st visit in our center), V2 (6 months follow-up) and V3 (1 year follow-up).
- MRI studies. It is a passive examination, patients will not need substantial mental or physical efforts. Total time ~45min during V2 (6 months follow-up).
- PSG: It is a passive examination, patients will not need substantial mental or physical efforts. Patients will sleep in the same room where the other clinical examinations and psychophysical testing will be carried out, so they will get used to and adjust to the environment during the day. Total time: night sleep during V1 (1st visit in our center), V2 (6 months follow-up) and V3 (1 year follow-up).
- ANS: It is an active examination. Patients will perform simple and non invasive exercises regarding deep breathing, blowing and standing up.
- EMG: It is a passive examination, patients will not need substantial mental or physical efforts.
- Brainstem reflex: It is a passive examination, patients will not need substantial mental or physical efforts.
- EEG: It is a passive examination, patients will not need substantial mental or physical efforts. Total time ~45min during V1 (1st visit in our center), V2 (6 months follow-up) and V3 (1 year follow-up).
- Actimetry: It is a passive examination, patients will not need substantial mental or

physical efforts. Total time: one week after V1 (1st visit in our center), V2 (6 months follow-up) and V3 (1 year follow-up).

- Lumbar Puncture will be performed, after informed consented, one at the first presential visit (V1) and the other at the last presential visit (V3).
- Brain recordings - It is a passive examination, patients will not need substantial mental or physical efforts. Total time: night sleep.
- Patients' blood and serum will be examined at the time of diagnosis (sent from local hospitals to our center via courier) and at the post-acute stage: V1 (1st visit in our center), V2 (6 months follow-up) and V3 (1 year follow-up). It will be performed in the same room; total time ~30min

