- b) Risks of Magnetic Resonance Imaging (MRI): The known risks associated with MRI studies are minimal. The procedure uses radio waves and a magnetic field to take pictures. Some individuals may feel claustrophobic (uncomfortable in small areas) during the MRI scan or may be disturbed by the sounds of the machine (which are loud and repetitive). Patients can be given music to listen to during the scan or can hear the voice of the technician. These have been shown to help patients relax during the scan. If the subject experiences these feelings and is uncomfortable, they can always discontinue the scan
- c) Risks of presential EEG studies: EEG is considered a safe procedure and causes no discomfort. During the recording, subjects can relax. Some people may develop a mild rash where the electrodes were attached that resolves without treatment.
- d) Risks of presential ANS, EMG and brainstem reflex: These neurophysiological tests are considered safe procedures which are performed daily in our centre. Discomfort related to electrical stimulation and needle insertion is minimal.
- e) Risks of presential Sleep studies: The same for EEG studies, as well as possible discomfort before falling asleep and reduced night rest. However, the cabling system is optimized to facilitate the free movement of patients at night, and the room is soundproofed.
- f) Risks of Psychophysical testing and Brain recordings: These evaluations are innocuous and do not represent any substantial risk for participants. The main risk of these evaluations is fatigue, reduced night rest, and they may be demanding in terms of execution time. However, they will only be performed in the course of two weeks separated by 6 months, for each participant. The computerized task will have a game component to make it engaging, as well as the device is specifically designed to be comfortable during sleep for nocturnal recordings. In the first day of the week of recordings, a member of our team will make a video-conference with the participant (including family members if they are minors) to assist with the setup of the device for testing and recording.
- g) Risks of Blood Tests: Risks associated with blood drawing include infection, bleeding, bruising, fainting and discomfort.

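### Actimeter wear is described only from leaving the hospital; if the device is fitted only at discharge, no night has both actimetry and video-polysomnography

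*Protocol*

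**What the plan says.** Section 4.1, item 1.5, provides an actimeter at each in-person visit, without giving the hour. It then says that "patients will leave the hospital with the device placed in the non-dominant wrist and in use" and describes one week of day-and-night wear at home after V1, V2 and V3. Section 7 (Presential visits, Actimetry) agrees: "Total time: one week after V1 (1st visit in our center), V2 (6 months follow-up) and V3 (1 year follow-up").

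Item 1.5 gives the goal as finding out whether home actimetry shows abnormalities that correlate with seizures and sleep alterations, such as awakenings and fragmentation, seen at the visit and on video-polysomnography. The Justification (section 2, first challenge) adds a purpose: actimetry "may help to track these nocturnal seizures at home, an observation that we propose to assess in the current proposal".

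On the reference recording, section 7 says: "Each visit consists of ~1 day and 1 night at Hospital Clínic (distributed in 1/2 day, 1 night, and 1/2 day"). Polysomnography takes place on that one night at V1, V2 and V3. Under item 1.2 it includes EEG and audiovisual recording, with sleep stages scored manually in 30-second epochs.

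**The concern.** Polysomnography is the study's reference for what happens during sleep. As the text stands, it is recorded on one night in hospital and actimetry on later nights at home. A patient-level association can still be estimated, but a weak one would have at least two explanations that the data could not separate: the device misses or misreads events, or the patient slept differently on another night in another place. The protocol's own risk section allows for the second, listing for the sleep study "as well as possible discomfort before falling asleep and reduced night rest".

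The seizure purpose raises a further question: does the device register a seizure when one occurs? Home nights cannot answer it, because no reference recording is tied to them. Patient or family report is a poor substitute, since the Justification says: "The main reason for the symptoms being unnoticed was that they often occurred at night or were identified with EEG or video-polysomnography".

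This is a matter of data collection. An analysis plan written later cannot recover nights on which the two devices were not running together.

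**Working it through.** No sample-size, power or error-rate figure bears on this point, so there is no figure of the protocol to reproduce. The check compares the two recording windows and counts nights.

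**Inputs**
- Patients: 20 (section 6).
- Visits with polysomnography: 3, namely V1, V2 and V3 (section 7).
- Polysomnography nights per visit: 1 (section 7, visit layout of half a day, one night, half a day).
- Actimetry: 1 week, taken as 7 nights, after each of the 3 visits (item 1.5 and section 7).

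**Order of events within one visit, as described**
1. Half a day in hospital.
2. The polysomnography night.
3. Half a day in hospital.
4. The patient leaves with the actimeter in use.
5. One week of wear at home.

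The described actimetry window opens at step 4 and the reference recording ends with step 2. The described windows do not overlap.

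**Counts, assuming full attendance and wear**
- Polysomnography nights: 20 x 3 x 1 = 60.
- Home actimetry nights: 20 x 3 x 7 = 420.
- Nights for which the text describes both recordings: 0.
- Nights with both if the actimeter is fitted before step 2: up to 20 x 3 = 60, or 3 per patient.

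**Does another recording supply the missing reference?** Section 7 lists a further night-time item: "Brain recordings - It is a passive examination, patients will not need substantial mental or physical efforts. Total time: night sleep". Section 9 (Risks, item f) says of the psychophysical testing and brain recordings that "they will only be performed in the course of two weeks separated by 6 months". That is two weeks, against three actimetry weeks. The protocol does not tie them to the actimetry weeks, does not call them polysomnography and does not mention seizure scoring. They cannot be counted as a same-night reference.

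**Is hospital-night wear ruled out?** No. The device is issued at the visit, and being in use on departure fits placement before the night as well as placement at discharge. The visit summaries in section 7 leave out other procedures too, so the absence of actimetry there proves nothing.

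**The case against.** The strongest reply is that comparing home with hospital is the declared aim of item 1.5 and the design delivers it. That stands: the correlation is testable as planned and the protocol does not contradict itself. Item 1.5 does not promise event-by-event validation of the device, and section 2 claims only that actimetry may help.

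The second reply is that the gap rests on silence. That also stands in part. A reader might infer that the actimeter is definitely absent on the polysomnography night, but the text does not say so. What it does do is let staff fit the device at discharge and still comply, which would lose every paired night.

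Third, the setting effect may be small. The protocol adapts the recording to the patient's sleep habits (item 1.2), has patients spend the day in the room where they will sleep (section 7), and describes cabling that allows free movement and a soundproofed room (section 9, item e). These measures reduce the difference between hospital and home, but they do not remove it, and they do nothing about variation from night to night.

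Fourth, the remedy tests the device only in hospital, while section 2 is about home. That is correct. After the change, all 420 home nights would still lack a reference. A reader might hope that the paired nights would establish how well the device detects seizures at home; they would not.

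**Conclusion.** The point holds as an optional improvement. Wear is described only from departure; if that is also when the device is fitted, 0 of up to 60 polysomnography nights carry actimetry. A weak home-to-hospital correlation could not then be divided between device error and a different night and setting, and the nocturnal-seizure use would have no time-matched check. The counts assume 20 patients, full attendance and full wear.

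It would go too far to conclude that the actimetry aim cannot be tested, or to say by how much the correlation would be weakened. The protocol gives no night-to-night reliability and no number of seizure nights, so neither the loss nor the precision of any seizure-level result can be calculated.

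The consequence is limited: actimetry is a listed study variable but is not named in the three objectives of section 4, and the comparison of patients with and without cognitive training does not depend on it.

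**What to change.** In item 1.5 and section 7, state that the actimeter already issued at the visit is fitted during the half-day before the video-polysomnography night at V1, V2 and V3, with its clock synchronised to the polygraph. Add this to the section 7 visit summaries and leave the home week unchanged. If hospital-night wear is already intended, one sentence saying so, plus the clock synchronisation, is enough.

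Compare actimetry with the time-matched scored epochs for awakenings and fragmentation, allowing for clustering by patient. Compare it descriptively with any seizures recorded that night. State that this checks the device in hospital only, that home nights remain without a reference, and that seizure-level accuracy may be imprecise.

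The cost is one extra night of wear per visit, a clock synchronisation and some time-stamping of events on the polysomnography. No extra visit or device is needed. The firmer gain is for awakenings and sleep fragmentation; the gain for seizures depends on how many happen to be recorded.

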1.6. Serum and CSF biomarkers of autoimmunity/inflammation and neuronal degeneration. Left over samples of blood and CSF that were obtained and stored during the acute stage of the disease (by the time of symptom onset and local hospital admission) will be obtained from the core laboratory (CBD) for patients seen at our center or will be sent to our center from the referring doctors. The diagnosis of anti-LGI1 encephalitis requires demonstration of antibodies in CSF (serum can be negative); thus, initial CSF studies form part of standard of care in this disease. For the current study, the left-over routine care serum and CSF samples from the recruited patients will be used after their informed consent. For patients followed at our institution, we will take advantage of a regular follow-up visit to inform about the study and obtain their consent. For patients cared for at other hospitals, the referring doctors will explain the possibility of participating in the current study and, if the patients consent, we will contact them to provide further explanations and in such case obtain the informed consent. Serum and CSF collection procedures will be as performed in the routine clinical practice of these patients. These acute samples will be tested for the indicated (see below) biomarkers of autoimmunity, inflammation, and neuronal injury. We are a referral center for the diagnosis and study of this disease, and therefore we have ample experience in receiving and handling the samples.

During the post-acute stage (by the time that patients will come to Hospital Clínic de Barcelona), blood and CSF samples will be obtained for identical studies as those performed in the acute stage serum and CSF samples. Two lumbar punctures will be performed, after informed consent, one at the first presential visit (V1) and the other at the last presential visit (V3).. Based on a recently published pilot study and extensive experience with the disease, all patients at V1 have cognitive, sleep and epileptic alterations and most still have residual deficits at V3; thus, the CSF studies are important for investigations on biomarkers of disease severity, outcome and prognosis, and for better optimization of therapeutic options. They include:

- LGI1 Antibodies, determined with brain tissue immunohistochemistry and cell-based assays.

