- HLA genotyping, performed by standard techniques based on DNA-PCR and polymorphism identification by reverse hybridization with specific probes and fluorescence labelling of hybridized fragments (PCR-SSOP) (Immucor GTI Diagnostics Inc. Waukesha USA) in combination with genomic DNA sequencing by Sanger methodology (PCRSBT).
- RNA/NanoString analysis of targeted gene expression related to activation/function of B cells, T cells, microglia, and other interleukin/ chemokine signaling. Whole blood/CSF will be collected using PAXgene® Blood RNA tubes (Qiagen) shipped to the centers. Total RNA will be extracted using PAXgene® Blood RNA Kit (Qiagen). RNA samples are quantified using Qubit 2.0 Fluorometer (Life Technologies) and RNA integrity is determined with Agilent 2100 Bioanalyzer

(Agilent Technologies). Expression levels of 44 genes related to immunological pathways and cytokines (Annex, Table) will be measured with the nCounter® Digital Analyzer (NanoString), as reported (*Armangue et al., Mol Genet Metab 2017;122:134-9*). Twenty healthy participants will serve as controls (single evaluation).

- NfL levels, determined in serum and CSF using the SiMoA Quanterix technique, as reported (*Guasp et al., Neurology 2022;98:e1489-98*). Age- and sex-matched healthy participants from previous studies will serve as controls. These studies will provide a signature of molecular biomarkers in the acute and chronic stages. We expect they will correlate with the clinical features assessed in Aim1 and will assist in treatment decisions.

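### The protocol does not fix one sample type for RNA: acute blood RNA is either unobtainable by the stated method or inseparable from sample type in patients without an acute PAXgene whole-blood sample

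*Protocol*

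**What the plan says.** The relevant text is mostly in Protocol section 4.1, item 1.6.

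- **Acute material.** It is introduced as "Left over samples of blood and CSF that were obtained and stored during the acute stage of the disease". The sentence that says what will be used is narrower: "the left-over routine care serum and CSF samples from the recruited patients will be used after their informed consent". On how it is drawn: "Serum and CSF collection procedures will be as performed in the routine clinical practice of these patients".
- **Tests on acute material.** "These acute samples will be tested for the indicated (see below) biomarkers of autoimmunity, inflammation, and neuronal injury". The list that follows contains LGI1 antibodies, HLA genotyping, RNA/NanoString and NfL. RNA is not exempted.
- **Post-acute material.** New samples are drawn at the study centre: "blood and CSF samples will be obtained for identical studies as those performed in the acute stage serum and CSF samples".
- **RNA method.** "Whole blood/CSF will be collected using PAXgene® Blood RNA tubes (Qiagen) shipped to the centers", with extraction by the matching kit. Twenty healthy people, evaluated once, are the controls; their sample type is not given.
- **Deliverable.** "These studies will provide a signature of molecular biomarkers in the acute and chronic stages".

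Two other places name the material differently. Objective 1 (section 4) puts RNA/NanoString among serum biomarkers. The calendar (section 7) has blood and serum examined at diagnosis, couriered from the local hospitals.

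**The concern.** The acute samples are described as what routine care left over, yet they are promised the same RNA study as samples that need a dedicated RNA-stabilising tube. For blood, both statements cannot hold unless someone draws a research tube in the acute phase, and no passage says that this happens.

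At stake is the acute part of the RNA signature. A difference in gene expression between a stored serum sample and a later PAXgene whole-blood sample could reflect the disease, the fluid, the tube or the storage. No later analysis plan can undo this, because sample type is settled when the sample is taken. Biomarkers belong to hypothesis 1 and objective 1, and the protocol expects them to inform treatment decisions, so the acute part should either be sound or not be promised.

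**Working it through.** The protocol gives no power, effect size or SD for the RNA panel, so there is no figure to reproduce. The check sets the passages side by side and then asks what can be estimated.

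**1. RNA sample type by place in the protocol**

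- Section 4, objective 1: serum.
- Section 4.1, item 1.6, acute, opening sentence: left-over blood and CSF.
- Section 4.1, item 1.6, acute, sentence on use: left-over routine serum and CSF.
- Section 4.1, item 1.6, post-acute: new blood and CSF.
- Section 4.1, item 1.6, RNA bullet: whole blood/CSF in PAXgene tubes.
- Section 7, at diagnosis: blood and serum.

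No place says that acute whole blood goes into a PAXgene tube, limits RNA to the post-acute visits, or allows for a difference in sample type.

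**2. What a blood RNA comparison would estimate**

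For one gene let S = 0 in the acute stage and 1 post-acute, and M = 0 for stored serum and 1 for PAXgene whole blood. Write expression as patient level + βS + γM + error, where β is the stage effect and γ the effect of sample type, tube and storage.

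- Patient without an acute PAXgene sample, if the stored serum is assayed: acute (S, M) = (0, 0), post-acute (1, 1). The expected difference is β + γ. S and M are the same indicator, so no model fitted to these patients separates them.
- Patient with an acute PAXgene sample: acute (0, 1), post-acute (1, 1). The expected difference is β.
- If k of the 20 patients have such a sample and all 20 have a pair, the average difference is β + γ(20 − k)/20. It is β + γ at k = 0 and β at k = 20. The protocol does not give k.
- If the stored serum cannot be processed by the stated method, the 20 − k patients have no acute blood RNA. The result is then missing, not biased.

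**3. What is not affected**

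- Blood RNA across V1, V2 and V3: M = 1 at each visit if the stated tube is used throughout, so γ cancels.
- CSF RNA: the fluid is CSF in both stages, so any γ comes from collection and storage only. V1 against V3 is like with like.
- LGI1 antibodies and NfL: these can be compared serum with serum and CSF with CSF.
- Healthy controls: a comparison with V1 to V3 is sound if their RNA comes from the same sample type and tube, which should be stated.

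**The case against.** The strongest reply is that acute PAXgene draws are intended. The opening sentence of item 1.6 says blood, and so does section 7. The tubes go to centres in the plural, although section 5 describes a single-centre study and all post-acute draws are at that centre; the plural may well mean the referring hospitals. Section 6 has patients approached during the acute phase. This stands as a possible reading, and for patients so sampled it removes the problem. It does not remove the contradiction, because a dedicated research tube is not a routine left-over.

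The timing of consent does not settle the matter either way. The sentence "we will take advantage of a regular follow-up visit to inform about the study and obtain their consent" applies only to patients followed at the sponsor's own institution. For referred patients no such visit is named, so one cannot conclude that no patient could have an acute tube.

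It is also fair that section 8 names no human test of acute against post-acute RNA; the explicit comparison of the two stages in section 4.1 is for mice (item 2.3). For patients the comparison is only implied by the signature sentence together with the promise of identical studies. How such a test would be run may be left to an analysis plan. Which fluid and tube are collected may not.

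**Conclusion.** The passages conflict and must be reconciled. Followed as written, acute blood RNA is either unobtainable by the stated method or, if run on stored serum, fully aliased with sample type, in every patient without an acute PAXgene whole-blood sample.

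A reader might infer that the whole RNA comparison between stages is confounded in all patients. The documents do not support that. Some acute PAXgene draws are conceivable, the number of patients without one is not stated, CSF is the same fluid at both stages, and missing data is as likely an outcome as bias. Nor can one say how many of the 44 genes would be wrongly linked to stage: the protocol gives nothing on the size of a sample-type shift, and any count would rest on an invented one and on whether the Bonferroni rule in section 8 covers the panel.

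The point is minor. It concerns an exploratory biomarker and leaves the V1 to V3 RNA course, antibodies, NfL and the cognitive-training comparison intact.

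**What to change.** Reconcile objective 1 (section 4), item 1.6 (section 4.1) and the diagnosis entry in section 7:

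1. State the RNA sample type and tube for the acute stage, for V1 to V3 and for the 20 healthy controls.
2. Limit any acute against post-acute comparison of blood RNA to patients who have an acute PAXgene whole-blood sample, and report how many there are.
3. Compare CSF RNA across stages only where collection and storage match.
4. Otherwise analyse blood RNA as change over V1 to V3 and against controls in the same sample type.
5. Restrict the signature sentence to markers measured in the same sample type at both stages.

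This is wording, with no new procedure. The cost is that the acute RNA comparison will have fewer patients, possibly none. It helps most if made before samples are collected.
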